8.1.4 Drug Accountability

Agent Inventory Records – The investigator, or a responsible party designated by the investigator, must maintain a careful record of the inventory and disposition of anastrozole.

8.2 Entinostat

8.2.1 Description

Entinostat is a synthetic small molecule bearing the chemical name N-[[4-[(2-aminophenyl)amino]carbonyl]phenyl]methyl]-, 3- pyridinylmethyl ester and the molecular formula $C_{21}H_{20}N_4O_3$, with a molecular weight of 376.41. SNDX-275 or MS-275 or Entinostat is classified as an anti-neoplastic agent, specifically functioning as an inhibitor of histone deacetylases by promoting hyperacetylation of nucleosomal histones, allowing transcriptional activation of a distinct set of genes that leads to the inhibition of cell proliferation, induction of terminal differentiation, and/or apoptosis.

8.2.2 Formulation

Entinostat is orally bioavailable and is supplied as light brown or yellow coated tablets containing 1 mg and 5 mg of active ingredient, respectively. Each tablet contains mannitol, carboxymethylstarch sodium, hydroxypropyl cellulose, potassium bicarbonate, and magnesium stearate as inactive ingredients. The tablet coat contains hydroxypropyl-methyl cellulose, talc, titanium dioxide, and ferric oxide pigment as a coloring agent.

8.2.3 Availability and Storage

Entinostat is an investigational agent supplied by Syndax Pharmaceuticals, Inc.

Entinostat is supplied as 1 mg (light brown, in bottles of 40), or 5 mg (intense yellow, in bottles of 40) film-coated tablets (round-biconvex). Each tablet also contains mannitol, carboxymethyl starch sodium, hydroxypropyl cellulose, potassium bicarbonate, and magnesium stearate, hydroxypropyl methylcellulose, talc, titanium dioxide, iron oxide pigment (yellow) and iron oxide pigment (red).

Entinostat tablets may be shipped and stored at room temperature (15-30°C), and should be protected from light. Avoid temperature extremes. The pharmacist will dispense the investigational material to the patient at appropriate intervals throughout the study in childproof containers. Shelf life stability studies of the intact bottles are on-going.

8.2.4 Drug Accountability

Agent Inventory Records – The investigator, or a responsible party designated by the investigator, must maintain a careful record of the inventory and disposition of entinostat.

8.3 Tamoxifen

8.3.1 Description

Tamoxifen or Nolvadex® is a nonsteroidal antiestrogen. It is the trans-isomer of a triphenylethylene derivative. The chemical name is (Z)-2-[4-(1,2-diphenyl-1-butenyl) phenoxy]-N, N-dimethylethanamine 2-hydroxy-1,2,3-propanetricarboxylate (1:1) with a molecular weight of 563.62.

8.3.2 Formulation

The tablets are round, biconvex, uncoated, white tablet identified with NOLVADEX 604 debossed on one side and a cameo debossed on the other side. Each tablet contains 20 mg equivalent of tamoxifen.

8.3.3 Availability and Storage

Tamoxifen will be prescribed by the treating physician and covered by the patients insurance.

These tablets should be stored at controlled room temperature 20-25°C (68-77°F). Dispense in a well closed, light-resistant container.

Additional information regarding the formulation as well as storage and handling instructions can be found in the approved package insert.

9. CORRELATIVE STUDIES

Both blood samples and tissue samples should be collected from both pilot and phase II subjects.

9.1 Tumor Tissue Samples

The submission of pathology materials from **BOTH** the original diagnostic procedure and the definitive surgery or biopsies are required for **ALL** patients.

9.1.1 Collections

In the first cohort:

Tumor tissue samples from the following time points will be obtained:

1. Prior to starting treatment or tissue sample at the original diagnostic procedure. (T0)
2. At the time of definitive surgery (i.e., mastectomy or lumpectomy). A separate tumor biopsy is not needed on the day of surgery; tissue will be taken from the surgical specimen. (T1)

Note: If a subject receives additional preoperative treatment after discontinuing study treatment and prior to surgery, every attempt should be made to collect a tissue sample for the study prior to initiation of the new treatment; in these cases, tissue will still be collected at the time of definitive surgery, as above.

Every effort should be made to provide a core specimen from the surgical sample after treatment. The site pathologist should remove a core samples during the dissection of the surgical specimen (using a 5-mm skin punch biopsy device). The samples should be processed preferably within 1 hour, but may be processed up to 2 hours of removal from the patients. This core specimen should be fixed in formalin and processed separately as per the American Society of Clinical Oncology/College of American Pathologists Guideline Recommendations published in Journal of Clinical Oncology 2010⁴².

In the second cohort:

Approximately six core biopsy specimens will be obtained with each biopsy. Alternative to core needle biopsy, fine needle aspirate (FNA) is allowed in this cohort of patients. Cytology cell blocks should be made from FNA specimens using routine institutional cytology protocol. Biopsy should be obtained from soft tissue metastasis such as breast, liver, skin, lung, or intra-abdominal implants. Bone biopsy, paracentesis (ascites), and thoracocentesis (pleural effusion) specimens are not adequate.

Tumor tissue samples from the following time points will be obtained:

1. Pretreatment biopsy (biopsy#1) will be performed within 3 weeks after registration. However, the pretreatment biopsy can be omitted in patients who have recent biopsy but have not been started on breast cancer treatment within 12 weeks prior to the registration and there is adequate tumor tissue sample as per section 3.1.9. (T0-Second cohort)
2. Post-treatment biopsy (biopsy#2) will be performed after a minimum of 15 days and a maximum of 29 days of treatment, but preferably close to 29 days. The post-treatment biopsy must take place within 6 days (preferably within 3 days) after the last dose of entinostat. If a patient discontinues the study prior to 15 days, an attempt should be made to collect the biopsy when the decision is made to discontinue and prior to initiation of additional treatment, if possible.

9.1.2 Paraffin Embedded Tissue Submission

All samples must be submitted **within ONE month** after the patient's definitive surgery or biopsy. All materials must be labeled with the institutional surgical pathology number, the study number, the patient's study number, the cohort number (first or second), the treatment group (tamoxifen or anastrozole), and the designated specimen type (T0 or T1). The samples should not contain patients' identifying information.

Please be sure to use a method of shipping that is secure and traceable. Extreme heat precautions should be taken when necessary. Please use papers to pad the specimen shipments. Do not use bubble wrap. Shipping should be arranged only on Monday-Thursday by overnight service to assure receipt. **Do not ship specimens on Friday or Saturday**. Please notify all of the contact persons listed below via email and/or telephone **PRIOR** to shipping.

A copy of the tissue tracking form should be included in the shipping package. Please note that if multiple samples are sent, only one copy of the form needs to be included.

The specimens should be shipped as directed below:

Specimens	Purpose	Shipping Address and Contact Information
≥3 unstained slides*	ER, PR, HER2, EGFR, CK5/6, Aromatase, histone H3, H4 acetylation, and Ki67 expression by immunohistochemistry NOTE: A copy of the pathology report from the treating and/or referring institution and a copy of the operative report should be included	[name], HT (ASCP) Pathology Biorepository and Research Core University of Maryland Medical Center [name] [name] 21201 [contact] [contact] Email: [contact]

	in this package.	
Tumor/lymph node block or ≥ 3 unstained slides[∞]	Gene expression profiling and Methylation profiling	[name]. Sidney Kimmel Comprehensive Cancer Center at Johns Hopkins [name] [contact] [contact] Email: [contact]

*Five-micron (5 μ M) thickness mounted on charged slides (do not oven bake slides) from both original diagnostic tumor blocks **AND** residual primary tumor or a positive lymph node blocks should be submitted as described above.

[∞]The original diagnostic tumor block and at least one representative block of residual primary tumor or a positive lymph node containing the maximum amount of tumor are required. Although it is preferred that tissue blocks are submitted, for institutions that do not allow submission of the tissue blocks, please submit ≥ 3 unstained sections of 5 μ M thickness mounted on charged slides.

9.1.3 Methods

9.1.3.1 Immunohistochemistry

Immunohistochemistry (IHC) will be used to determine the pre-treatment and post-treatment expression of ER, PR, HER2, and Ki67. The level of expression of these proteins will be quantified by ChromaVision ACIS Assisted Quantitative Image Analysis. These studies will be performed by immunohistochemistry technicians in the pathology department at the University of Maryland which is certified by both Clinical Laboratory Improvement Amendments (CLIA) and College of American Pathologists (CAP). The specimens will be de-identified with a unique patient's study number and stored in the tumor bank facility at University of Maryland. Hematoxylin and eosin stained sections will be examined by a pathologist to confirm the tissue source. Five-micron sections of formalin-fixed, paraffin-embedded tissue will be tested for the presence of immunohistochemically detectable ER, PR, HER2, and Ki67 expression. After 60 minutes of heat induced epitope retrieval in citrate buffer, streptavidin biotin detection systems using Ventana reagents and instruments will be used. We will use ER, PR, HER2, Ki67, EGFR, and CK5/6 antibodies that have been validated and are currently in clinical use at University of Maryland pathology department as listed below.

Immunostaining	Antibody
ER	SP1 rabbit monoclonal Ventana prediluted anti-ER antibody
PR	1E2 rabbit monoclonal Ventana prediluted anti-PR antibody
HER-2	4B5 rabbit monoclonal Ventana prediluted anti-HER-2/neu antibody
Ki67	30-9 rabbit monoclonal Ventana prediluted anti-Ki67 antibody
EGFR	3C6 mouse monoclonal Ventana prediluted anti-EGFR antibody
CK5/6	D5&16B4 mouse monoclonal Ventana prediluted anti-CK5/6 antibody
Aromatase	Mouse monoclonal antibody (Novartis #677) ⁴³

Scoring systems:

- ER and PR: Will be scored as the percentage of positive staining tumor nuclei on the examined slide. Five percent immunoreactivity is considered a positive result. This is based on comparison of our results to that of clinically validated ER and PR assays, determined by several large clinical studies.
- HER-2/neu: Will be scored as followed - score 0: no membrane staining is observed. 1+: weak, incomplete staining in any proportion of the invasive tumor cells. 2+: complete membrane staining in less than or equal to 30% of the invasive tumor cells. 3+: strong complete membrane staining in more than 30% of the invasive tumor cells.

- Ki-67: Will be assessed by counting 500 to 1000 cells, and will be reported as percent positive cells based on nuclear expression using ChromaVision ACIS system to quantify.
- EGFR: Will be assessed by counting 500 to 1000 cells, and will be reported as percent positive cells based on membrane expression using ChromaVision ACIS system to quantify.
- CK5/6: Will be assessed by counting 500 to 1000 cells, and will be reported as percent positive cells based on cytoplasmic expression using ChromaVision ACIS system to quantify.
- Aromatase: Will be assessed by counting 500 to 1000 cells, and will be reported as percent positive cells based on cytoplasmic expression using ChromaVision ACIS system to quantify.

Various other cancer specimens (expression in > 30% of the tumor cells) will be used as positive controls. Buffer will replace primary antibody for negative controls. All of the immunohistochemical staining will be quantitatively analyzed by ChromaVision ACIS system for immunohistochemistry image analysis. Quantitation of both staining intensity as well as assessment of numbers of positive stained cells will be determined by the agreement of a consensus of pathologists and researchers. These studies will be carried out under the direction of [name] in the Department of Pathology at University of Maryland.

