12. STATISTICAL CONSIDERATIONS

12.1 Study Design/Endpoints

This is a Pilot and Phase II, single-arm, open-labeled, multi-center study of entinostat in combination with anastrozole/tamoxifen in women with triple negative breast cancer. The main objective of this study is to assess the safety and efficacy of the combination of entinostat and anastrozole/tamoxifen. The primary endpoints, that we will use to evaluate the efficacy of the entinostat and anastrozole/tamoxifen, are the reduction in proliferative index (Ki67) and upregulation of ER after treatment with entinostat and anastrozole/tamoxifen therapy. We define patient's response as at least 50% reduction in the Ki67 index AND greater than 1% ER-positivity OR pathologic complete response in the post-treatment surgical specimens. For the evaluation of these biological endpoints, the analysis will include ALL of the patients in both cohorts (the first cohort-operable stage I-II and the second cohort-unresectable locally advanced/metastatic) as well as both anastrozole and tamoxifen groups.

In the pilot phase, the classic cohort-of-3-study design will be used. The primary endpoint of this part of the study is to determine the recommended dose for the phase II part as well as to evaluate the safety of both combinations. The dose levels are defined below for both pre- and postmenopausal groups. For safety, each combination (entinostat and anastrozole as well as entinostat and tamoxifen) will be evaluated separately. For both groups (anastrozole and tamoxifen), the first cohort of 3 patients will be treated starting at dose level 1 (d_1). If ≤ 1 patient experiences DLT, an additional 3 patients will be treated at this dose level (d_1). If ≥ 2 patients in the initial cohort of 6 patients suffer DLT, then up to 6 additional patients will be enrolled at the dose level -1. The phase II part will continue with the highest dose level with < 2 out of 6 patients experiencing a DLT. Therefore, we will need 6-12 patients for each combination

in this part of the study. The 6 patients from the pilot phase of each combination that are treated with the recommended dose level for the phase II will be included in the primary endpoint analysis.

The dose modification schemas are as follow for both postmenopausal and premenopausal women:

Dose Modification Schema for Postmenopausal Women		
Dose Level	Dose	
	Entinostat (mg)	Anastrozole (mg) daily
-1	3 mg weekly (on day 1, 8, 15, 22, and 29)	1

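### No step masks the Ki67 and ER readers to time point, although labels and enclosed reports carry it and a human consensus settles the reads in a single-arm trial

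*Combined protocol and SAP*

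**What the plan says.** - **Labels.** Section 9.1.2 requires each tissue sample to show, among other items, the cohort, "the treatment group (tamoxifen or anastrozole), and the designated specimen type (T0 or T1").
- **Meaning of the codes.** For the first cohort, section 9.1.1 defines the first time point as "Prior to starting treatment or tissue sample at the original diagnostic procedure. (T0") and says of the second: "A separate tumor biopsy is not needed on the day of surgery; tissue will be taken from the surgical specimen. (T1"). The code therefore states before or after. For the second cohort, section 9.1.1 codes the pretreatment biopsy as T0 and gives no code for biopsy #2, but the labelling rule in 9.1.2 still applies to all materials.
- **Enclosures.** The row of the 9.1.2 shipping table for the immunohistochemistry slides adds: "A copy of the pathology report from the treating and/or referring institution and a copy of the operative report should be included" in that package.
- **Scoring.** Section 9.1.3.1 states: "All of the immunohistochemical staining will be quantitatively analyzed by ChromaVision ACIS system for immunohistochemistry image analysis". It then says that quantitation of intensity and assessment of positive-cell numbers "will be determined by the agreement of a consensus of pathologists and researchers".
- **De-identification.** Section 9.1.3.1 also says: "The specimens will be de-identified with a unique patient's study number". This conceals the patient, not the time point.
- **Design.** Section 12.1: "This is a Pilot and Phase II, single-arm, open-labeled, multi-center study". Response is a Ki67 fall of at least 50% together with ER above 1%, or pathologic complete response. The trial stops if none of the first 12 patients responds, and the combination is called promising if at least 4 of 32 respond.

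The documents contain no instruction to recode slides, mask readers to time point, or randomise the reading order.

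**The concern.** In a single-arm before-after comparison, any systematic difference between how pre-treatment and post-treatment slides are read goes straight into the treatment effect. No control arm is read the same way to cancel it.

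Three features of this plan make that relevant:

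- The expected direction is set out in the protocol's own rationale (sections 2.5 and 2.6): Ki67 down, ER up.
- Both components are cut-offs. Eligibility (3.1.4) requires ER below 1%, so the ER component turns on the post-treatment read. The 50% Ki67 cut-off sits at the upper end of the 32-50% change that section 2.6 cites as needed before a change in one patient can be attributed to treatment.
- The go rule needs only 4 responders in 32, so one or two reclassified patients can decide the result.

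What is at stake is the false-positive rate of the go decision. The stated operating characteristics assume that response is classified without bias.

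**Working it through.** **Inputs.** From section 12.1: 12 patients in stage 1, stop at 0 responses; 20 more in stage 2; promising if at least 4 of 32 respond; uninteresting rate 5%, target rate 20%.

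**Step 1: reproduce the stated design.**

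P(go | p) = Σ over x from 1 to 12 of P(Bin(12, p) = x) × P(Bin(20, p) ≥ 4 − x)

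P(early stop | p) = (1 − p)^12

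At p = 0.05:

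- x = 1: 0.3413 × 0.0755 = 0.0258
- x = 2: 0.0988 × 0.2642 = 0.0261
- x = 3: 0.0173 × 0.6415 = 0.0111
- x ≥ 4: 0.0022
- Sum: 0.065

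| Quantity | Plan | Computed |
|---|---|---|
| P(go) at 5% | 0.07 | 0.065 |
| P(go) at 20% | 0.87 | 0.866 |
| Early stop at 5% | 0.54 | 0.95^12 = 0.540 |
| Early stop at 20% | 0.07 | 0.80^12 = 0.069 |

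The stated figures are reproduced.

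**Step 2: illustrate a net upgrade of the composite call.** Let f be the probability that a true non-responder is scored as a responder on the whole composite because of how the slides were read. The documents give no value for f, so the values below are assumptions. The scored response rate at a true 5% is p = 0.05 + 0.95f. The expected number of misread patients among 32 is 32 × 0.95 × f.

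| f (assumed) | p scored | Misread of 32 | Early stop | P(go) |
|---|---|---|---|---|
| 0 | 0.0500 | 0 | 0.540 | 0.065 |
| 1% | 0.0595 | 0.30 | 0.479 | 0.107 |
| 2.5% | 0.0738 | 0.76 | 0.399 | 0.186 |
| 5% | 0.0975 | 1.52 | 0.292 | 0.345 |

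**Step 3: illustrate a tilt at one cut-off only.** Response through the biomarkers needs both components, so an error at one cut-off changes the call only for a non-responder who already meets the other. Let s be the share of non-responders who do. It is not in the documents either; I take 10% to 30%. Then p = 0.05 + 0.95 × f × s.

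| f (assumed) | s (assumed) | p scored | P(go) |
|---|---|---|---|
| 2.5% | 10% | 0.0524 | 0.075 |
| 2.5% | 30% | 0.0571 | 0.095 |
| 5% | 10% | 0.0548 | 0.085 |
| 5% | 30% | 0.0643 | 0.131 |

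Under these assumptions a one-sided tilt moves P(go) from 0.065 to between 0.075 and 0.131, well below the 0.186 and 0.345 of step 2 for the same f.

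**The case against.** **Image analysis is a safeguard.** All staining goes through ACIS, Ki67 is counted on 500 to 1,000 cells, and the laboratory is CLIA- and CAP-certified. The consensus sentence could mean no more than agreeing the software's output. This stands in part: it limits how far a reader can move a score, by an unknown amount. But the text gives the determination of both intensity and positive-cell numbers to a group that includes researchers, so it does not make the read automatic.

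**The readers may never see the label.** A reader might infer that Ki67 and ER are in fact read with knowledge of the time point. The documents do not say so. The labelling rule governs submission to the biorepository, and no sentence describes what is visible on the slide or image at the moment of scoring. What can be said is that the information travels with the tissue and its paperwork, and that nothing stops it reaching the readers.

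**One small tilt does not make a responder.** A reader might also infer that bias at either cut-off turns non-responders into responders. The definition joins Ki67 and ER with AND, so a patient who fails both needs two favourable errors, and the pathologic complete response route uses neither score. This objection stands, and is why step 3 is set beside step 2.

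**Treatment group on the label matters little.** Anastrozole and tamoxifen patients are pooled for the primary analysis, and knowing which was given does not separate before from after. This is correct; the time point is what matters.

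**Masking may not be complete.** In the first cohort the post-treatment tissue comes from the surgical specimen and may be distinguishable from a diagnostic core even after recoding. This also stands, as a limit on the remedy.

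**Conclusion.** The point holds as a gap in procedure: time point, cohort and treatment group are on every tissue label, the clinical reports travel with the slides, a human consensus settles the scores after image analysis, and no step masks the readers. The paired Ki67 and ER reads are therefore open to reading bias in a design with no control arm. The documents do not show that bias will occur, or how large it would be.

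The size is illustrative only. P(go) at a true 5% rate is 0.065 without bias. It rises to 0.107, 0.186 or 0.345 if f, defined as the net false upgrade of the composite call, is 1%, 2.5% or 5%. If one cut-off alone is tilted in 2.5% to 5% of non-responders and 10% to 30% of them already meet the other component, the range is 0.075 to 0.131. Both f and s are assumptions.

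This is a cheap improvement that protects the stated error rate, not a fault in the design arithmetic, which reproduces.

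**What to change.** Amend sections 9.1.2 and 9.1.3.1 so that:

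1. The biorepository recodes each slide with a random number that does not reveal time point, cohort or treatment group, and holds the key.
2. The pathology and operative reports stay with the biorepository and are withheld from those who score Ki67 and ER.
3. Each patient's T0 and T1 slides are stained in one batch and read in random order.
4. The key is released only after the Ki67 and ER scores are locked.

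Sample size, stopping rule, stated power and patient procedures do not change. The cost is a relabelling step at the central laboratory and some delay while pairs are batched. The report should acknowledge that masking may be incomplete in the first cohort because surgical tissue can look different from a core.

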9.1.3.2 Gene Expression Profiling

Additional biopsy for fresh tissue sample is not required in this study. We will use the cDNA-mediated Annealing, Selection, Extension, and Ligation (DASL) assay from Illumina which has been developed to allow more comprehensive gene expression profiling of degraded RNA extracted from paraffin blocks using bead array format as previously described³⁷. Illumina's Bead Array Technology is based on 3-micron silica beads that self assemble in microwells on either of two substrates: fiber optic bundles or planar silica slides. When randomly assembled on one of these two substrates, the beads have a uniform spacing of ~5.7 microns. Each bead is covered with hundreds of thousands of copies of a specific oligonucleotide that act as the capture sequences in one of Illumina's assays. BeadArray technology is utilized in Illumina's iScan System for a broad range of DNA and RNA analysis applications.

All promising findings of gene expression changes will also be validated by the quantitative RT-PCR methods. Change in expression of genes as a result of treatment will be determined by IHC or quantitative RT-PCR. Although IHC can be easily accomplished on a single slide, it may not be sensitive to small changes in expression and expression measurements are semi-quantitative. Quantitative (real-time) RT-PCR can provide better quantification of expression of gene product, and recent studies have shown that this approach can be applied to RNA isolated from paraffin-embedded tissues, when small sequences are amplified. The overall goal of these studies is to identify candidate markers for response and molecular profiles that might be relevant to an understanding of drug mechanisms. Although statistical methods will provide some indication of significance of particular molecular changes, validation will ultimately require additional testing in independent samples.

